6.1 Study treatment

In this study, the terms “investigational drug”, “study drug” or “study treatment” refers to the oral co-administration of LDE225 QD and INC424 BID administered to patients daily. The investigational treatment for this trial, which is the drug combination whose properties are being tested in this study, is LDE225 and INC424.

6.1.1 Dosing regimen

Table 6-1 Dose and treatment schedule

| Study treatments | Pharmaceutical form and route of administration | Dose | Frequency and/or Regimen |
|------------------|---|--|--------------------------|
| LDE225 | Capsule for oral use | Starting dose 400 mg to be increased or decreased per Bayesian design (see Section 6.2.1) | Once a day/QD |
| INC424 | Tablet for oral use | Starting dose 10 mg to be increased per Bayesian design (see Section 6.2.1) | Twice a day/BID |

Patients should be instructed to take their daily dose of LDE225 once in the morning and INC424 twice a day, at approximately the same time each day. Each daily dose of LDE225 (including days which involve PK blood sampling) must be taken approximately 2 hours after a light breakfast (e.g., consisting of milk, toast and jam). For example, if breakfast was completed at 08:00 a.m., then study drug administration should occur at 10:00 a.m. Patients must also then fast from food and drinks (except water) for 1 hour following dosing. A light snack may be taken if absolutely necessary (eg, crackers or toast), but high-fat meals must be avoided for 2 hours before and 1 hour after each dose. INC424 can be taken with or without food, therefore the morning dose of INC424 can be taken concurrently with LDE225. The afternoon/evening dose of INC424 can be taken with or without food, approximately 12 hours after the morning dose. LDE225 and INC424 should be taken with a glass of water and should be swallowed whole. Patients must avoid consumption of Seville (sour) oranges/ juice, grapefruit products/juice, grapefruit hybrids, pummelos and exotic citrus fruits during the

entire study and preferably 7 days before the first dose of study medications, due to potential CYP3A4 interaction with the study medications. Orange juice is allowed.

If the patient forgets to take his/ her daily LDE225 dose, then they should take it within 6 hours after the missed dosing time. If more than 6 hours have passed, then that day's dose must be omitted and the patient should continue treatment with the next scheduled dose.

If a patient misses a dose of INC424, then he/she should take INC424 within 3 hours after the missed dose. If more than 3 hours have passed, then that missed dose should be omitted and the patient should continue treatment with the next scheduled dose. Patients should not take 2 doses at the same time.

Patients should inform the investigational site staff of any missed or delayed doses.

If vomiting occurs during the course of the study treatment, then no re-dosing of the patient is allowed before the next scheduled dose. The occurrence and frequency of any vomiting must be noted in the adverse events section of the eCRF.

On days when pre-dose PK sampling is required, the patient should take his/her dose at the clinic after the sampling and a light meal. The patient must not eat until instructed to do so at the clinic.

6.1.2 Ancillary treatments

Not applicable.

6.1.3 Rescue medication

Not applicable.

6.1.4 Guidelines for continuation of treatment

For guidelines on the continuation of treatment, refer to [Section 6.3](#) Dose modifications.

6.1.5 Treatment duration

The planned duration of treatment is at least 2 years. Patients may be discontinued from treatment with the study drugs due to documented disease progression, intolerable toxicity, withdrawal of consent, discontinuation at the discretion of the investigator, or lost to follow-up, whichever comes first. Patients who complete 2 years of treatment and are deriving clinical benefit in the opinion of the investigator will be allowed to continue receiving treatment (LDE225 and INC424) in an extension phase of this study, until discontinuation reasons are met or an alternative setting to receive study treatment (e.g., in form of another protocol) becomes available.

The extension phase will begin on the day after the Week 105 visit. The first extension phase visit will occur 12 weeks after the Week 105 visit. See [Table 7-2](#) for the schedule of assessments during the study extension phase.

A safety follow-up will be conducted 30 days (+3 days) after the last dose of study medication is received and a study completion form will be completed in the eCRF. The safety follow-up

may be waived if the patient is continuing on INC424 and LDE225 treatment in an alternative setting.

6.2 Dose escalation guidelines

6.2.1 Starting dose rationale

INC424 as a single agent has been tolerated up to doses of 25 mg BID and a minimum 25% reduction in splenomegaly was seen in the majority of patients treated at 10 mg BID, 15 mg BID, and 25 mg BID (Verstovsek 2010). From [INCB018424-251] and supported by results from [CINC424A2352] (See Section 1.4.2.2.3), 15 mg BID and 20 mg BID were established as the most effective and safest starting doses followed by individualized dose titration (Verstovsek 2010).

LDE225 as a single agent has been evaluated in dose levels of 100, 200, 400, 800, 1000, 1500 and 3000 mg QD, and 250, 400 and 750 mg BID. Based on the available data from [CLDE225X2101], the maximum tolerated dose of LDE225 in adult patients is 800 mg QD. Since this is the first study of LDE225 in combination with INC424, starting doses that are lower than the respective MTDs and/or clinically approved doses have been chosen as LDE225 400 mg QD plus INC424 10 mg BID.

The starting dose and regimen are considered safe. In addition, no drug-drug interaction is expected from the combination.

The starting doses for each drug have been selected based on prior monotherapy experience where these doses have shown some degree of clinical activity as single agents and pharmacodynamic data supports the activity observed. In the interest of patient safety, both of these compounds will start at dose levels at or near 50% of their respective maximum tolerated doses. The provisional doses for dose escalation are shown in Table 6-2.

6.2.2 Provisional dose levels

The first cohort will start at low doses for both drugs (LDE225 at 400 mg QD and INC424 at 10 mg BID). The doses will then be escalated following the recommendation of an adaptive Bayesian logistic regression model for dose escalation with overdose control (EWOC) until the MTD and/or RPIID is defined.

Dose escalation will be guided by the following considerations:

- At all decision time points, the adaptive Bayesian logistic model permits alterations in the dose increments based on the observed DLTs. Only one of the 2 combination partners can be escalated and the maximum inter-cohort dose escalation is limited to 100%, i.e. up to 100% and 0% increase for LDE225 and INC424 respectively or 0% and up to 100% increase for LDE225 and INC424 respectively.
- The proposed combination meets the EWOC criteria (i.e. less than 25% chance that the true rate of DLT lies within the interval [35% - 100%]).
- If at any time $\geq 35\%$ of patients in a cohort experience a DLT and 2 or more DLTs have occurred in that cohort, one of the following actions will be implemented:
 1. Reduce the dose of one of the combination partners or both and enroll a new cohort

2. Termination of any further escalation of the combination partners

If two MTDs/RPIIDs are established all patients in Phase II will receive the corresponding dose based on their platelet status. The selected action may only be permitted if the respective dose combination satisfies the overdose control criteria.

Table 6-2 describes the starting dose and the dose levels that may be evaluated during this trial.

Table 6-2 Provisional dose levels

| Dose level | Proposed daily dose* | Increment from previous dose |
|-------------|------------------------------------|------------------------------|
| Cohort -1** | INC424 10 mg BID, LDE225 200 mg QD | -50% LDE225 dose |
| Cohort 1 | INC424 10 mg BID, LDE225 400 mg QD | (starting dose) |
| Cohort 2 | INC424 15 mg BID, LDE225 400 mg QD | +50% INC424 dose |
| Cohort 3 | INC424 15 mg BID, LDE225 800 mg QD | +100 % LDE225 dose |
| Cohort 4 | INC424 20 mg BID, LDE225 800 mg QD | +33% INC424 dose |

*Depending on the emerging data, it is possible to explore other combination dose levels without exceeding the highest admissible combination dose-level per the BLRM. Thus, intermediate dose levels other than those listed above may be evaluated.

**Dose level -1 represents the treatment dose for patients requiring a dose reduction from the starting dose level. No dose reduction below dose level -1 is permitted for this study, however if patients experience thrombocytopenic DLTs in Cohort 1 then those patients will receive INC424 5 mg BID and LDE225 200 mg QD.

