6.3 Dose modifications

6.3.1 Dose modification and dose delay

For patients who do not tolerate the protocol-specified dosing schedule, dose adjustments are permitted in order to allow the patient to continue the study treatment. The following guidelines need to be applied. Any plan to deviate from these guidelines in view of patient safety must be discussed with the sponsor unless there is an urgent need for action.

All dose modifications should be based on the worst preceding toxicity as graded by the NCI Clinical Toxicity Criteria (NCI-CTCAE version 4.03). If study treatment is held due to toxicity, scheduled visits and all assessments as described in [Table 7-1](#) should continue as scheduled, except without dosing. Dose modification guidelines are described in [Table 6-4](#).

If an adverse event is clearly associated to one of study drugs, the dose adjustment directed for that study drug will be followed; however, if the causality is not clear, then it may be necessary to adjust both study drugs. Dosing adjustments will be discussed with the sponsor.

If a patient experiences a DLT then treatment with LDE225 plus INC424 must be stopped and the patient may be discontinued from the study. However, following resolution of the DLT to CTCAE grade 1 or to the patient's baseline value, the patient may continue to receive study treatment at a reduced combination dose level, if appropriate, at the discretion of the investigator and after discussion with the Sponsor.

For each patient, a maximum of 2 dose reductions will be allowed, after which the patient will be required to discontinue study treatment. If the same toxicity returns after re-initiation of treatment at the same dose level, the second re-initiation must resume at a lower dose level. The patient must also discontinue study treatment if, after the treatment is resumed at the lower dose level, the same toxicity recurs with the same or worse severity (except for thrombocytopenia, anemia and neutropenia).

Dose level (-1) is the lowest acceptable dosing level for a patient participating in the study. If a patient cannot tolerate dose level (-1), then study treatment must be discontinued and the patient must be withdrawn from the study. However, if patients in Cohort 1 experience thrombocytopenic DLTs then patients in dose level (-1) will receive INC424 5mg BID and LDE225 200 mg QD.

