| Febrile neutropenia (Grade \geq 3) (ANC < $1.0 \times 10^9/L$, with a single temperature of ≥ 38.3 °C or a sustained temperature of ≥ 38 °C for more than one hour) | INC424: Discontinue study treatment LDE225: Discontinue study treatment |
| Thrombocytopenia (for 2 consecutive assessments within 48 hrs) | |
| Grade 1 (PLT < LLN - $75 \times 10^9/L$) | INC424: Maintain dose level LDE225: Maintain dose level |
| Grade 2 (PLT < $75 - 50 \times 10^9/L$) | INC424: Reduce to 10 mg BID or continue at same dose level (whichever is lower) LDE225: Maintain dose level |
| Grade 3 (PLT < $50-25 \times 10^9/L$) | INC424: Reduce to 5mg BID LDE225: Maintain dose level |
| Grade 4 (PLT < $25 \times 10^9/L$) | INC424: Hold dose until resolved to \leq grade 1, then maintain dose level LDE225: Hold dose until resolved to \leq grade 1, then maintain dose level |
| Hemorrhagic event of any kind (if related to study treatment) | |
| Grade 1 | INC424: Maintain dose level LDE225: Maintain dose level |
| Grade 2 | INC424: Hold dose until resolved completely, then \downarrow by 5 mg BID LDE225: Hold dose until resolved completely, then maintain dose level |
| Grade 3 or 4 | INC424: Discontinue study treatment LDE225: Discontinue study treatment |
| RENAL | |
| Serum creatinine | |
| < 2 x ULN | INC424: Maintain dose level LDE225: Maintain dose level |
| 2 – 3 x ULN | INC424: Hold dose until resolved to \leq grade 1, then: If resolved in \leq 7 days, then maintain dose level If resolved in > 7 days, then \downarrow by 5 mg BID LDE225: Hold dose until resolved to \leq grade 1, then: If resolved in \leq 7 days, then maintain dose level If resolved in > 7 days, then \downarrow 1 dose level |
| Grade 3 (> $3.0 - 6.0 \times ULN$) | INC424: Discontinue study treatment LDE225: Discontinue study treatment |
| Grade 4 (> $6.0 \times ULN$) | INC424: Discontinue study treatment LDE225: Discontinue study treatment |

| | |
|--|---|
| Dose modifications for toxicities occurring during the DLT-definition period (6 weeks or 42 days), and considered as treatment-related, will not be allowed until the toxicity qualifies as a DLT. | |
| Worst toxicity (CTCAE 4.03 Grade) | Dose Modifications for INC424 and LDE225 |
| HEPATIC | |
| Bilirubin (*for patients with Gilbert Syndrome these dose modifications apply to changes in direct bilirubin only). Bilirubin will be fractionated if elevated | |
| Up to 2.0 x ULN | INC424: Maintain dose level LDE225: Maintain dose level |

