7.1.3 Discontinuation of Study Treatment

Patients may voluntarily discontinue from study treatment for any reason at any time. If a patient decides to discontinue from the study treatment, the investigator must make every effort (e.g., telephone, e-mail, letter) to determine the primary reason for this decision and record this information in the patient's chart and on the appropriate eCRF pages. Patients may be considered withdrawn if they state an intention to withdraw, fail to return for visits, or become lost to follow-up for any other reason.

The investigator should discontinue study treatment for a given patient if he/she believes that continuation would be detrimental to the patient's well-being.

Study treatment must be discontinued under the following circumstances:

- Emergence of the following adverse events:
 - Grade 3 or 4 hemorrhagic event of any kind
 - Grade 3 renal toxicity for ≥ 7 consecutive days
 - Grade 4 renal toxicity
 - Grade 4 non-hematologic toxicity
 - Second occurrence of QTcF > 500 ms (\geq Grade 3) or > 60 ms change from baseline on at least two separate ECGs
 - Patient requires or undergoes splenic irradiation
 - Patient requires or undergoes splenectomy
- Any of the following laboratory abnormalities:
 - Grade 4 anemia for ≥ 7 consecutive days despite PRBC transfusions
 - Febrile neutropenia (Grade ≥ 3) (ANC $< 1.0 \times 10^9/L$, with a single temperature of ≥ 38.3 °C or a sustained temperature of ≥ 38 °C for more than one hour)
 - Grade 3 or 4 serum creatinine
 - Bilirubin $> 10.0 \times ULN$
 - Grade 3 or 4 asymptomatic or symptomatic CK elevation with renal function impairment in which CK and creatinine levels do not return to baseline after interrupting treatment
- Pregnancy

- The following deviations from the prescribed dose regimen for LDE225 and INC424:
 - Interruption of study treatment for > 21 days, regardless of reason, from the intended day of the next scheduled dose. However, if the patient is obtaining clinical benefit in terms of response, the patient may continue treatment at the same or at a reduced dose following discussion between the investigator and Novartis.
 - If after 2 dose reductions and after the treatment has resumed at the lower dose, the same toxicity recurs with the same or worse severity (except for thrombocytopenia, anemia, and neutropenia)

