 - If a patient cannot tolerate dose level (-1), which is the lowest acceptable dosing level for this study, except for patients in Cohort 1 who experience thrombocytopenic DLTs and can receive INC424 5mg BID and LDE225 200mg QD.
- Disease Progression
- Use of prohibited treatments (refer to Appendix 1) as determined by Novartis
- Use of another myeloproliferative neoplasm directed therapy
- Any other protocol deviation that results in a significant risk to the patient's safety
- Study is terminated by the Sponsor

Patients who discontinue study treatment should NOT be considered withdrawn from the study. They should return for the assessments indicated in [Table 7-1](#) and [Table 7-2](#). If they fail to return for these assessments for unknown reasons, every effort (e.g. telephone, email, letter) should be made to contact them as specified in [Section 7.1.5](#).

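### The dose floor and the dose-modification tables contradict each other: level -1 is the stated minimum, yet Tables 6-4 and 6-6 send patients to INC424 5 mg BID

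*Protocol*

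**What the plan says.** **The floor.** Protocol Table 6-2 defines level -1 as "INC424 10 mg BID, LDE225 200 mg QD". The footnote adds "No dose reduction below dose level -1 is permitted for this study", and Section 6.3.1 agrees: "Dose level (-1) is the lowest acceptable dosing level for a patient participating in the study". Section 7.1.3 lists intolerance of level -1 among the mandatory reasons to stop treatment.

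**The one exception.** The Table 6-2 footnote continues "however if patients experience thrombocytopenic DLTs in Cohort 1 then those patients will receive INC424 5 mg BID and LDE225 200 mg QD". Section 7.1.3 words it as "except for patients in Cohort 1 who experience thrombocytopenic DLTs". In Table 6-3 thrombocytopenia is a DLT only at Grade 4.

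**The tables.** For Grade 3 thrombocytopenia on two consecutive assessments within 48 hours, Table 6-4 says "INC424: Reduce to 5mg BID LDE225: Maintain dose level". Table 6-6, for restarts after a Grade 4 hold, begins INC424 at 5 mg BID when platelets are 50 to <75 x10^9/L or ANC is 0.5 to <0.75 x10^9/L, with LDE225 at its original level. Neither table names a cohort or phase. Modifications are barred in the 6-week DLT-definition period unless the event is a DLT.

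**Stopping rules.** Section 6.3.1 says "a maximum of 2 dose reductions will be allowed, after which the patient will be required to discontinue study treatment". It also stops treatment when the same toxicity recurs at the lower level with the same or worse severity, cytopenias excepted. Section 7.1.3 has a different trigger: "If after 2 dose reductions and after the treatment has resumed at the lower dose, the same toxicity recurs", with the same cytopenia exception. Section 6.3.1 withdraws from the study a patient who cannot tolerate level -1, whereas Section 7.1.3 says that patients who discontinue treatment are not to be considered withdrawn.

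**The concern.** Two sets of rules govern the same event and give different instructions. Thrombocytopenia is a common reason for changing the INC424 dose: Section 1.4.2.2.1 reports reductions or interruptions for it in 32.4% of myelofibrosis patients on INC424. The same section gives a median onset of Grade 3 or 4 thrombocytopenia of 8 weeks, which is after the 6-week restricted period and before the Week 24 scan. Phase II is dosed at LDE225 400 mg QD plus INC424 20 mg BID (Amendment 2 rationale), so its patients fall outside the Cohort 1 exception.

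At stake are consistent dosing across sites and, in a narrower group, the primary endpoint. Where one reading keeps a patient on treatment and the other stops treatment and ends participation, Week 24 or Week 48 response can depend on the section followed.

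**Working it through.** **1. Is 5 mg + 400 mg below level -1?** Compare it with 10 mg + 200 mg, drug by drug: INC424 5/10 = 0.5 and LDE225 400/200 = 2. It is lower in one drug and higher in the other, and the documents do not rank such pairs. The written exception (5 mg + 200 mg) differs from level -1 only in INC424, so the protocol treats that step as needing express permission. This favours a per-drug reading but does not settle it.

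**2. Four patients under both sets of rules** (confirmed Grade 3 thrombocytopenia, after Week 6):

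| Patient | Table 6-4 | Floor | Does the floor order a stop? |
|---|---|---|---|
| A: Phase II, 20 mg BID + 400 mg | 5 mg + 400 mg | 5 mg excluded if the floor is per drug; undetermined if per combination | No; level -1 has not been reached |
| B: already cut to 10 mg at Grade 2, LDE225 400 mg | 5 mg + 400 mg | No lower INC424 step if per drug | Not until level -1 is not tolerated |
| C: at level -1, outside Cohort 1 | 5 mg + 200 mg | Below the floor on either reading | Yes, if level -1 is not tolerated |
| D: Cohort 1, 10 mg BID + 400 mg | 5 mg + 400 mg | Exception does not apply, because Grade 3 is not a DLT; otherwise as A | No |

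The dose instruction is in doubt for A, B and D. Only C faces a stay-or-stop split. For B, the steps 20 to 10 mg and 10 to 5 mg make two reductions, and the two-reduction cap in Section 6.3.1 carries no cytopenia exception, although the recurrence rule does.

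**3. Stopping rules for non-exempt toxicities.** A patient reduced once whose toxicity recurs at the lower level with the same severity must stop under the 6.3.1 recurrence rule. Under the 7.1.3 item the patient has not yet had two reductions and need not stop.

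**4. Link to the endpoint.** A patient like C becomes a non-responder through this conflict only if the stop comes before the Week 24 (or Week 48) visit and the patient then drops out or has no scan (protocol Section 10.4.3; SAP Section 3.5.3). A stop after the Week 24 scan leaves that result intact. The disagreement over study status matters here, because a patient kept in the study may still be scanned.

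**5. The plan's figures.** The design figures reproduce and do not depend on this conflict. P(success) is the sum over x = 8 to 18 of P(X1 = x) P(X2 >= 23 - x), with X1 ~ Bin(18, p) and X2 ~ Bin(28, p). This gives 0.0952 at p = 0.40 and 0.9004 at p = 0.60, against the stated 9.5% and 90%. The SAP table for 20 patients also reproduces with the Beta(1,1) prior, summing the beta-binomial over y >= 23 - x with m = 26: 0.325 for 9 responders and 0.149 for 8. At that boundary one responder crosses the 20% threshold.

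**6. Illustration only.** Let f be an assumed share of would-be Week 24 responders lost under the stricter reading. The effective rate is q = 0.60(1 - f):

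| f | q | P(at least 9 of 20) |
|---|---|---|
| 0 | 0.600 | 0.943 |
| 2% | 0.588 | 0.930 |
| 5% | 0.570 | 0.904 |
| 10% | 0.540 | 0.849 |
| 20% | 0.480 | 0.687 |

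Nothing in the documents fixes f.

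**The case against.** The best defence is that much of this is ambiguity. Section 6.3.1 itself points to Table 6-4 for modifications and has dosing adjustments discussed with the sponsor. A note to Table 6-4 allows case-by-case discussion. The Table 6-2 footnote describes reductions from the starting dose level, and 5 mg + 400 mg is not clearly lower than 10 mg + 200 mg. The Stage 1 decision is also already made: SAP Sections 1.1 and 3.5.2.1 record that Stage 2 was not started.

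Part of this stands. The defence limits the consequence, and new wording cannot change the Stage 1 count. It does not remove the conflict. The case-by-case note concerns departures from the table's recommendation and does not say whether the table or the floor governs, and Section 12 bars investigators from asking for approval of deviations. For a patient at level -1 outside the exception, Table 6-4 gives 5 mg + 200 mg, which is below the floor on either reading.

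A reader might infer three stronger things that the documents do not support:

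- **That every Grade 3 patient outside Cohort 1 must stop under the floor.** The trigger is intolerance of level -1. A Phase II patient on 20 mg BID can be reduced as far as that level without stopping. The Table 6-4 row also needs two assessments and does not operate in the first 6 weeks, since Grade 3 thrombocytopenia is not a DLT.
- **That stopping equals non-response.** It does so only through drop-out or a missing scan before the visit.
- **That the historical rates give a count of lost responders.** The 32.4% mixes reductions with interruptions. The 35.4% and 64.2%, for baseline platelets above 200 and 100 to 200 x10^9/L, pool Grade 3 with Grade 4, which has its own row. None says how many patients would reach level -1, fail it and miss a scan.

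**Conclusion.** The inconsistency is real and the rules cannot all be followed as written. The Table 6-2 footnote, Section 6.3.1 and Section 7.1.3 set a floor with one narrow exception, and Tables 6-4 and 6-6 use INC424 5 mg BID without regard to it. Sections 6.3.1 and 7.1.3 also differ on recurrence, on the number of reductions and on study status. The dose conflict reaches Phase II.

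The effect on the primary endpoint is confined to patients who reach level -1, cannot tolerate it, and drop out or miss a scan before Week 24 or Week 48. Its size cannot be computed from the documents, and the table over f rests wholly on assumption. The stated type I error and power are correct, and nothing shows that the no-go decision would have differed. This should be corrected because the rules still govern dosing in the open-ended extension and the response rate has yet to be reported in the CSR. It does not overturn a result.

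**What to change.** The sponsor must reconcile the Table 6-2 footnote, Section 6.3.1 and Section 7.1.3 with Tables 6-4 and 6-6. The revised text should:

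1. state how the floor is read for a two-drug combination (per drug or per pair), and whether it applies in Phase II;
2. give one rule for the number of reductions and the recurrence that end treatment;
3. give one rule on whether a patient who stops treatment remains in the study for scheduled assessments.

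Which dose rule applies is for the sponsor to decide; none is proposed here.

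In the CSR, list patients dosed below level -1, or stopped because of it, with the date of the change, whether the Week 24 and Week 48 scans were done, and response status. Keep the prespecified rule that a missing response is a non-response; unscanned patients should not be re-counted as responders.

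The cost is protocol wording and one extra listing.
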